7.3. Migraine and pregnancy outcomes

Migraine itself has been associated with an increased risk of some adverse pregnancy outcomes. A population-based cohort study using Danish population registries identified 22,841 pregnancies among women with migraine and an age- and conception year-matched comparison cohort of 228,324 pregnancies among women without migraine.¹⁵ Compared to the women without migraine, women with migraine, regardless of treatment type, were shown to have an increased risk of pregnancy-associated hypertension disorders and miscarriage, and an increased prevalence of low birth weight, preterm birth, and cesarean delivery, but not for small for gestational age (SGA) and MCMs. The prevalence of any MCM was 3.1% in women with and without migraine. Offspring who were prenatally exposed to maternal migraine had elevated risks of intensive care unit admission, hospitalization, dispensed prescriptions, respiratory distress syndrome, and febrile seizures, but not of death and cerebral palsy. The results suggested that migraine itself, rather than its treatment, is associated with adverse pregnancy and Infant outcomes.¹⁵

Other investigators have similarly reported associations between migraine and gestational hypertension, pre-eclampsia,¹⁶ low birth weight,^{8,16-18} and preterm birth.^{8,16} In earlier studies, women with migraine were reported to be at an increased risk of developing hypertensive disorders such as pre-eclampsia in pregnancy compared to women without migraine,^{19,20} which is associated with an increased risk of low birth weight, preterm birth, and SGA infants.²⁰⁻²² In the migraine population, more severe migraine,

PFIZER CONFIDENTIAL

defined by greater frequency and intensity, was shown to be associated with an increased prevalence of cardiovascular comorbidities and comorbid affective disorders such as anxiety and depression.^{23,24} In the US general population, the estimated background risk of MCMs and miscarriage in clinically recognized pregnancies is 2%–4% and 15%–20%, respectively. The estimated rates of MCMs (2.2% to 2.9%) and miscarriage (17%) among deliveries to women with migraine are similar to rates reported in women without migraine.¹⁴

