9.3.4.3. Pre-eclampsia

Pre-eclampsia will be defined as high blood pressure and signs of liver or kidney damage (eg, proteinuria) occurring at >20 gestational weeks.^{45,46}

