9.3.4.5. Gestational hypertension

Gestational hypertension will be defined as high blood pressure occurring at >20 gestational weeks without signs of liver or kidney damage (eg, proteinuria).⁴⁶

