9.3.4.6. Gestational diabetes

Gestational diabetes will be defined as any degree of glucose intolerance with onset or first recognition during pregnancy.⁴⁷

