9.3.5. Other variables

The following additional variables will be collected (or derived from collected data):

- Geographic region
- Calendar year at conception
- Maternal age at conception
- Maternal race
- Maternal ethnicity
- Proxies for maternal socioeconomic status, including maternal education, employment status, and income
- Maternal pre-pregnancy body mass index, calculated from pre-pregnancy weight and height
- Gestational age at registry enrollment
- Method of conception
- Number of fetuses
- Fetal/infant sex
- Concurrent maternal medical conditions, including thyroid abnormalities, infectious diseases, asthma, diabetes, hypertension, seizure disorder, autoimmune diseases, depression and other psychiatric disorders, hepatitis, sexually transmitted diseases, and uterine or cervical abnormalities (eg, congenital uterine abnormalities)

PFIZER CONFIDENTIAL

- Concurrent pregnancy-related maternal medical conditions or pregnancy complications, including gestational diabetes, gestational hypertension, pre-eclampsia, eclampsia, preterm labor, placental abruption, and incompetent cervix
- Number of previous pregnancies
- Previous pregnancy outcomes (SAB, stillbirth, elective termination, TOPFA, live birth)
- Previous pregnancy complications
- Characteristics of previous live births (preterm, SGA)
- Previous fetus/infant with congenital malformations (major and minor)
- Family history of congenital malformations (major and minor)
- Characteristics of migraine disease, including typical severity just prior to pregnancy (ie, to establish baseline severity) and duration (ie, time since diagnosis)
- Maternal exposure to other drugs or biological products, including prescription and non-prescription drugs, dietary supplements, and vaccines, during pregnancy and gestational age at exposure
- Maternal exposure to tobacco, alcohol, marijuana, and recreational or illicit drugs during pregnancy and timing of exposure

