Secondary analysis: among all pregnancy outcomes with exposure at any time during pregnancy (if applicable for cohort)	Live births and fetal losses with confirmed MCMs (excluding MCMs not associated with medication exposure) among women with pregnancy outcome data and, if applicable, exposure at any time during pregnancy	Live births and fetal losses among women with pregnancy outcome data and, if applicable, exposure at any time during pregnancy	

Table 4.	Calculation of Outcome Prevalence
----------	------------------------------------------

PFIZER CONFIDENTIAL

Outcome	Numerator	Denominator
Comparison with external comparator (CDC MACDP)	Live births and stillbirths with confirmed MCMs (including MCMs not associated with medication exposure) among women with pregnancy outcome data and exposure during the 1 st trimester	Live births among women with pregnancy outcome data and exposure during the 1 st trimester
Comparison with external comparator (Pfizer Study C4951006 [formerly BHVN Outcomes Study])	Live births with confirmed MCMs (excluding MCMs not associated with medication exposure) among women with pregnancy outcome data and exposure at any time during pregnancy	Live births among women with pregnancy outcome data and exposure at any time during pregnancy
Comparison with EUROCAT	Live births and stillbirths and TOPFA with confirmed MCMs (including MCMs not associated with medication exposure) among women with pregnancy outcome data and exposure during the 1 st trimester	Live births and stillbirths among women with pregnancy outcome data and exposure during the 1 st trimester
Secondary Outcomes		
Minor congenital malformations	Live births with minor congenital malformations among women with pregnancy outcome data	Live births among women with pregnancy outcome data
Gestational diabetes		
Primary analysis between internal cohorts	Gestational diabetes among women with pregnancy outcome data	Women with pregnancy outcome data
Comparison with external comparator (CDC NVSS)	Gestational diabetes among live births	Live births among women with pregnancy outcome data
Gestational hypertension		
Primary analysis between internal cohorts	Gestational hypertension among women with pregnancy outcome data	Women with pregnancy outcome data
Comparison with external comparator ⁶¹	Gestational hypertension among live births	Live births among women with pregnancy outcome data
Pre-eclampsia		

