Primary analysis between internal cohorts	Pre-eclampsia among women with pregnancy outcome data	Women with pregnancy outcome data
Eclampsia	·	
Primary analysis between internal cohorts	Eclampsia among women with pregnancy outcome data	Women with pregnancy outcome data
Comparison with external comparator ⁶¹	Eclampsia among live births	Live births among women with pregnancy outcome data
Pre-eclampsia/eclampsia	•	
Primary analysis between internal	Pre-eclampsia or eclampsia among	Women with pregnancy outcome

PFIZER CONFIDENTIAL

Outcome	Numerator	Denominator
cohorts	women with pregnancy outcome data	data
Comparison with external comparator (Pfizer Study C4951006)	Pre-eclampsia or eclampsia among women with pregnancy outcome data	Women with pregnancy outcome data
SAB		
Primary analysis between internal cohorts	SABs among women with pregnancy outcome data who are enrolled (and exposed, if applicable) prior to 20 gestational weeks	Women with pregnancy outcome data who are enrolled (and exposed, if applicable) prior to 20 gestational weeks
Comparison with external comparator (Pfizer Study C4951006)	SABs among women with pregnancy outcome data who are enrolled (and exposed, if applicable) prior to 20 gestational weeks	Women with pregnancy outcome data who are enrolled (and exposed, if applicable) prior to 20 gestational weeks
Stillbirth		
Primary analysis between internal cohorts	Stillbirths among women with pregnancy outcome data	Women with pregnancy outcome data
Comparison with external comparator (CDC NVSS)	Stillbirths among women with pregnancy outcome data	Live births and stillbirths among women with pregnancy outcome data
Comparison with external comparator (Pfizer Study C4951006)	Stillbirths among women with pregnancy outcome data	Women with pregnancy outcome data
Elective termination		
Primary analysis between internal cohorts	Elective terminations among women with pregnancy outcome data	Women with pregnancy outcome data
Comparison with external comparator (CDC Abortion Surveillance System)	Elective terminations among women with pregnancy outcome data	Live births among women with pregnancy outcome data
Comparison with external comparator (Pfizer Study C4951006)	Elective terminations among women with pregnancy outcome data	Women with pregnancy outcome data
TOPFA		
Primary analysis between internal cohorts	TOPFA among women with pregnancy outcome data	Women with pregnancy outcome data

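### Gestational hypertension is defined without a new-onset requirement, so pre-existing hypertension can be counted as an outcome; pre-eclampsia has the same gap in a much narrower form

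*Protocol*

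**What the plan says.** Section 9.3.4.5 of the protocol: "Gestational hypertension will be defined as high blood pressure occurring at >20 gestational weeks without signs of liver or kidney damage". Section 9.3.4.3: "Pre-eclampsia will be defined as high blood pressure and signs of liver or kidney damage (eg, proteinuria) occurring at >20 gestational weeks". Neither mentions new onset or normal blood pressure earlier in pregnancy. The next definition, gestational diabetes in Section 9.3.4.6, does have an onset condition: "any degree of glucose intolerance with onset or first recognition during pregnancy".

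For the internal comparison, Table 4 in Section 9.7.3.3 gives the numerators as "Gestational hypertension among women with pregnancy outcome data" and "Pre-eclampsia among women with pregnancy outcome data". The denominator for both is all women with pregnancy outcome data. The outcome-specific restrictions listed in that section concern malformations, preterm birth, small for gestational age, postnatal growth deficiency, developmental delay and spontaneous abortion. The exclusion criteria in Section 9.2.2 do not mention hypertension.

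Pre-existing hypertension is recorded. Section 9.3.5 lists "Concurrent maternal medical conditions, including thyroid abnormalities, infectious diseases, asthma, diabetes, hypertension, seizure disorder" and, as a separate item, pregnancy-related conditions including gestational hypertension and pre-eclampsia. Section 9.7.3.4.1 says that the Section 9.3.5 variables will be considered for the weighting model.

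**The concern.** A maternal complication outcome should count what arises in the pregnancy. As worded, Section 9.3.4.5 can also count a condition the woman brought into it.

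Two distortions could follow:

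- **Dilution.** If pre-existing hypertension is equally common in the two cohorts, it adds the same block of cases to both and pulls a real relative risk towards 1.
- **Imbalance.** If it is more common among exposed women, it raises the crude relative risk with no drug effect. The protocol gives some reason to think of this. Section 7.3 says that more severe migraine "was shown to be associated with an increased prevalence of cardiovascular comorbidities", and Section 9.9 says that severity may differ between the cohorts.

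Pre-eclampsia is less exposed, because liver or kidney signs are also needed. Only a woman whose organ signs pre-date the pregnancy, such as long-standing proteinuria, could be miscounted.

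**Working it through.** **Inputs from the protocol.** 390 women per cohort, relative risk 2.5, two-sided alpha 0.05, normal approximation (Section 9.5.2, Table 3). Reference rates are 6.5% for gestational hypertension and 3.40% for pre-eclampsia.

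**Inputs assumed.** The share *c* of women with chronic hypertension is not in the protocol; 3%, 5% and 8% are used here. The 6.5% is taken as a rate of new-onset disease only. Every woman with chronic hypertension is assumed to be counted as a case.

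**Step 1: the protocol's own figures.** The pooled normal approximation is z = [(p1 − p0)√n − 1.96√(2p̄(1 − p̄))] / √(p0(1 − p0) + p1(1 − p1)).

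- Gestational hypertension, 6.5% against 16.25%: power 99.1% (stated >99.0%).
- Pre-eclampsia, 3.4% against 8.5%: power 85.5% (stated 85.5%).

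Both reproduce, and neither is in dispute.

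**Step 2: equal chronic hypertension in both cohorts.** Observed rate = c + (1 − c) × true rate.

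- c = 3%: unexposed 0.03 + 0.97 × 0.065 = 0.0930; exposed 0.03 + 0.97 × 0.1625 = 0.1876; ratio **2.02**.
- c = 5%: unexposed 0.05 + 0.95 × 0.065 = 0.1118; exposed 0.05 + 0.95 × 0.1625 = 0.2044; ratio **1.83**.

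| c in both cohorts | Power, true RR 2.5 | Power, true RR 2.0 |
|---|---|---|
| 0% | 99.1% | 86.6% |
| 3% | 96.9% | 76.1% |
| 5% | 94.5% | 69.4% |

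**Step 3: unequal chronic hypertension, no true effect, unadjusted.**

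- 5% exposed, 3% unexposed: 0.1118 / 0.0930 = **1.20**.
- 8% exposed, 3% unexposed: (0.08 + 0.92 × 0.065) / 0.0930 = 0.1398 / 0.0930 = 1.50.

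**Step 4: if only some are miscounted.** Suppose, again by assumption, that 20% of women with chronic hypertension are recorded as gestational hypertension. The counted share becomes 0.2 × 3% = 0.6% or 0.2 × 5% = 1.0%.

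- 0.6% in both cohorts, true RR 2.5: (0.006 + 0.994 × 0.1625) / (0.006 + 0.994 × 0.065) = 0.1675 / 0.0706 = 2.37.
- 1.0% against 0.6%, no true effect: 0.0744 / 0.0706 = 1.05.

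**Step 5: pre-eclampsia.** The same formula applies with a 3.4% base rate and an assumed 0.1% to 1% of women having high blood pressure plus pre-existing organ signs. A true relative risk of 2.5 becomes 2.46 to 2.16, and power falls from 85.5% to between 84.9% and 79.6%.

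**The case against.** The best defence is that the registry would not apply the definition literally. No blood pressure readings are among the listed data items. Cases come from healthcare providers, who report chronic conditions (hypertension is named) and pregnancy complications as separate items. A provider with a known hypertensive patient has a proper place to record her. A condition called gestational, dated after 20 weeks, can also be read as meaning onset, and the cited guidance may say so. This stands as a reason to treat Steps 2 and 3 as upper bounds. It does not close the gap: the protocol states the case rule, and the rule lacks the condition that the diabetes definition includes. The independent case review in Section 9.4.4 and Section 11 covers malformations only.

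A second defence is the planned adjustment. Hypertension and baseline migraine severity are both candidate covariates for weighting, so the 1.20 and 1.50 are crude ratios that adjustment could shrink. That stands too, with two limits: the covariates are only to be considered, and weighting corrects imbalance but not dilution.

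A third is that operational case rules can be left to the SAP. But Section 9.3.4 already sets the definitions, so the SAP would have to amend them rather than fill a blank.

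A reader might go further and infer that chronic hypertension alone makes a woman a pre-eclampsia case. Section 9.3.4.3 does not support that: "Pre-eclampsia will be defined as high blood pressure and signs of liver or kidney damage" requires both elements. Nor do the documents support a forecast of a false signal. Section 7.3 speaks of cardiovascular comorbidity in general, not hypertension, and gives no rates by cohort.

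**Conclusion.** The gap is real for gestational hypertension and small for pre-eclampsia. The stated rule lets a pre-existing condition count as an outcome, and nothing in the eligibility criteria, Table 4 or the denominator rules prevents it.

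Under the assumed shares and full miscounting, the ceiling is a true relative risk of 2.5 seen as 2.02 to 1.83, or a crude 1.20 with no effect at 5% against 3%. The expected effect is smaller by an amount the protocol does not allow one to estimate. Even at that ceiling, power for a relative risk of 2.5 stays at 94.5% or more for shares up to 5%; the loss is more noticeable at a relative risk of 2.0.

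These are secondary outcomes with nominal p-values (Section 9.7). The primary malformation analysis and the sample size are untouched. The correction is worth making because it is cheap, not because the study's main conclusion depends on it.

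**What to change.** - **Section 9.3.4.5:** require high blood pressure with onset after 20 gestational weeks.
- **Table 4, internal comparison of gestational hypertension:** exclude women with hypertension recorded before pregnancy or before 20 weeks from both numerator and denominator.
- **Section 9.3.4.3:** require that the liver or kidney signs be new after 20 weeks. Do not require absence of pre-existing hypertension here. That would discard genuine pre-eclampsia superimposed on chronic hypertension and, because Section 9.3.4.4 defines eclampsia through pre-eclampsia, would also remove those women from eclampsia and the combined outcome. Keep superimposed cases in all three outcomes, and also tabulate them by pre-existing hypertension.

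The cost is wording and a slightly smaller denominator for gestational hypertension. Hypertension is already collected from the obstetric provider, so no new data item is needed to identify these women.

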9.3.4.6. Gestational diabetes

Gestational diabetes will be defined as any degree of glucose intolerance with onset or first recognition during pregnancy.⁴⁷

9.3.4.7. Preterm birth

Preterm birth will be defined as an infant born at <37 weeks gestational age. As cases of preterm birth accrue, and if appropriate, cases may be further classified by gestational age as: Extremely Preterm (<28 weeks), Very Preterm (28 to < 32 weeks), or Moderate to Late Preterm (32 to < 37 weeks).

9.3.4.8. Small for gestational age (SGA)

SGA will be defined as birth weight $<10^{\text{th}}$ percentile for sex and gestational age. For the determination of SGA, the registry will utilize the sex-specific international growth reference standards from the

PFIZER CONFIDENTIAL

International Fetal and Newborn Growth Consortium for the 21st Century (INTERGROWTH-21st) for infants born between 24^{0/7} and 42^{6/7} gestational weeks.^{48,49} The INTERGROWTH-21st standards are the latest-available, global reference standards, representing contemporary information from an international, multiethnic, diverse population, and have been specifically developed for modern research.

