7.2. Rimegepant and pregnant women

There are no adequate data on the developmental risk associated with the use of rimegepant in pregnant women. In animal studies, oral administration of rimegepant at high doses (300 mg/kg/day; exposures over 200 times that observed in humans administered at the therapeutic dose of 75 mg) during organogenesis resulted in adverse effects on development in rats (decreased fetal body weight and increased incidence of fetal variations). These highest-dose test exposures also resulted in maternal toxicity and were approximately 45 times the maximum recommended human dose.¹⁴

As of 31 May 2020, there were 32 women treated with rimegepant who reported pregnancies during the rimegepant clinical development program (in addition to 1 pregnancy reported in a partner assigned to rimegepant). Of these 32 treated women, 11 reported live births (in addition to 1 partner pregnancy), 6 reported spontaneous abortions (SABs), 3 reported elective abortions, 4 had subsequently negative urine or serum pregnancy test results, and the 8 remaining women had unknown pregnancy outcomes and/or only an approximate due date was reported with no further follow-up information. There were 4 women assigned to placebo who reported pregnancies (in addition to 1 partner pregnancy), 2 had subsequent negative urine pregnancy test results, and 1 had an unknown pregnancy outcome.

Lastly, a study of breastfeeding women (lactation) with rimegepant (BHV3000-115) was initiated in Jan 2020.

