Maternal Exposures during Pregnancy

Collected from participants in real time or near real time during pregnancy

- On a weekly basis, exposure to rimegepant or other acute migraine therapies (prescription and nonprescription), including name of product, dates of exposure, and total dose taken on each day of the week, if available
- On a monthly basis, exposure to rimegepant or other preventive migraine therapies (prescription and non-prescription), including name of product, dates of exposure, dose, route, and frequency

Collected from HCP(s)—obstetric and prescriber, if needed

- Exposure to drugs or biological products (including prescription and non-prescription drugs, dietary supplements, vaccines, and known teratogens), including indication/reason for use (for migraine products: acute only, preventive only, or both), dose, route, frequency, and dates/duration of exposure, if available
- Exposure to tobacco, alcohol, marijuana, or recreational or illicit drugs, including timing of exposure, if available

Ongoing pregnancy information

Collected from obstetric HCP; HCPs will only be asked for updates to the data previously reported

- Number of fetuses
- EDD and method of determination
- Prenatal tests performed, including type of test, date of test, and results/findings (eg, congenital malformations)
- Concurrent maternal medical conditions, including but not limited to migraine, diabetes, hypertension, depression
- Concurrent pregnancy-related maternal medical conditions or pregnancy complications

Pregnancy outcome information

Collected from HCP(s)—obstetric and pediatric, if needed

• Pregnancy outcome (SAB, elective termination, TOPFA, live birth, stillbirth)

PFIZER CONFIDENTIAL

- Date of pregnancy outcome
- Gestational age at outcome
- Fetal/infant characteristics, including sex, birth weight, length, head circumference
- Route of delivery
- Delivery/birth complications, if any
- 5-minute Apgar score
- Congenital malformation(s) and potential contributing factors
- For a fetal loss (SAB, stillbirth), factors that may have had an impact on the fetal loss
- For elective termination, reason
- For live birth, prolonged hospitalization after birth

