9.5.2. Full study

The full study will aim to prospectively enroll a minimum of 390 women with migraine who were exposed to rimegepant during pregnancy or just prior to pregnancy (up to 3 days prior to conception), as well as an internal comparison cohort consisting of 390 women with migraine who were not exposed to rimegepant during pregnancy or just prior to pregnancy (up to 5 product half-lives prior to conception). The target sample size for the registry is based on the primary outcome, MCM, which is also the outcome with the most restrictive denominators and 1 of the lowest prevalence rates in the general population. If all are evaluable for potential MCMs (evaluable being those for whom pregnancy outcome and major/minor congenital malformation assessments are obtained), and assuming an approximate 3% overall population prevalence of MCM, ⁵⁴ at α =0.05, this sample size provides 80% power to detect a 2.5-fold increased risk for overall MCM. Most registry power calculations are performed for overall MCM to detect an increased risk between 2- and less than 3-fold.⁵⁵ A midpoint threshold of a 2.5-fold increased risk was selected for this study. Assumptions for study calculations are consistent with those applied in the retrospective pregnancy outcomes study (NDA 212728, postmarketing requirement 3799-7, Pfizer study C4951006 [formerly BHV3000-403]).

Prospective enrollment can occur only after pregnancy is recognized but while the pregnancy is ongoing. Therefore, early pregnancy losses will not be captured, and a live birth rate higher than that of the general population would be expected. Research shows that approximately 90% of pregnancies enrolled in pregnancy exposure registries result in a live birth.^{56,57} Assuming that 90% of prospectively enrolled pregnancies result in live births and 10% are lost to follow-up,⁵⁸ at α =0.05, the study sample of 390 prospectively enrolled pregnant women in each internal cohort would result in 316 evaluable participants per cohort. Therefore, the study would have 80% power to detect a 2.7-fold increased risk of overall MCM (Table 2).

PFIZER CONFIDENTIAL

Outcome	N per cohort	Reference rate	Relative risk detectable	Power ^b
МСМ	390	3% ^{54,55,59}	2.5	80.6%
МСМ	316 ^a	3% ^{54,55,59}	2.7	80%

Table 2.	Sample Size and Power Estimates for Primary	Outcome, MCM

MCM = major congenital malformation; reference rate = prevalence rate of outcome in general population for pregnant women of any age

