9.7. Data analysis

Detailed methodology for the summary and statistical analyses of the data collected in this study will be documented in a statistical analysis plan (SAP), which will be dated, filed, and maintained by the Sponsor. The SAP may modify the plans outlined in the protocol; any major modifications of primary outcome definitions or their analyses would be reflected in a protocol amendment.

Descriptive analyses for the primary and secondary study objectives will be performed annually for all data; comparative analyses will be conducted for the final analysis.

Registry data will be summarized in tables and listings by study cohort, as appropriate. These data include maternal demographic characteristics and pre-pregnancy anthropometrics, pregnancy information, maternal obstetrical history, family history of congenital malformations, disease information, maternal exposures during pregnancy, pregnancy outcome information, and infant outcome information. For each continuous variable, the number of observations, median, mean, standard deviation, minimum, and maximum will be reported. For each categorical variable, the frequency and percentage in each category will be reported. The frequency and percentage of participants with missing data for each data point will be presented. Results will be rounded to one decimal place; therefore, percentages may not always add up to 100.

Pair-wise comparisons of demographic characteristics, baseline characteristics, and prevalence rates of the outcomes of interest will be conducted between the study cohorts: pregnant women with migraine who were exposed to rimegepant versus pregnant women with migraine who were unexposed to rimegepant.

Comparisons will be conducted using the methods described below, and p-values and 95% CIs will be reported, as appropriate, to reflect statistical uncertainty. The study is not powered for multiple comparisons; thus, p-values associated with secondary outcomes will be nominal. Additional details are provided below and will be provided in the SAP.

PFIZER CONFIDENTIAL

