9.7.3. Analysis of the outcome measures

9.7.3.1. Comparison with internal comparator cohorts

Formal quantitative comparisons of prevalence rates of the outcomes of interest will be conducted between the study cohorts. The prevalence rates of the outcomes of interest will be calculated as described in Section 9.7.3.3.

For each outcome, if the number of events permits, results will be presented for unadjusted and adjusted models. Summary statistics (relative risk) will be reported along with their 95% CIs and p-values. For the primary outcome, a p-value <0.05 will be considered statistically significant. Exact methods will be used to calculate crude (unadjusted) relative risks for binary outcomes, including MCM, minor congenital malformation, SAB, elective termination, TOPFA, stillbirth, pre-eclampsia, eclampsia, gestational hypertension, gestational diabetes, preterm birth, SGA, postnatal growth deficiency, and infant developmental delay.

Adjusted methods will incorporate weights estimated using the IPW method to balance the cohorts with regard to observable covariates (Section 9.7.3.4). For each binary outcome, a weighted generalized linear model using a binomial family and a log (relative risk) link will be employed to estimate an adjusted relative risk.

PFIZER CONFIDENTIAL

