Comparison with external comparator (EUROCAT) ⁴⁴	TOPFA among women with pregnancy outcome data	Live births and stillbirths among women with pregnancy outcome data
Preterm birth		
Primary analysis between internal cohorts	Singleton preterm live births without MCMs among women with pregnancy outcome data who are enrolled (and exposed, if applicable) prior to 37 gestational weeks	Singleton live births without MCMs among women with pregnancy outcome data who are enrolled (and exposed, if applicable) prior to 37 gestational weeks
Comparison with external comparator (Pfizer Study C4951006)	Preterm live births among women with pregnancy outcome data who are	Live births among women with pregnancy outcome data who are

PFIZER CONFIDENTIAL

Outcome	Numerator	Denominator
	enrolled (and exposed, if applicable) prior to 37 gestational weeks	enrolled (and exposed, if applicable) prior to 37 gestational weeks
SGA		
Primary analysis between internal cohorts	Singleton live births without MCMs who are SGA based on weight/length/head circumference among women with pregnancy outcome data	Singleton live births without MCMs with weight/length/head circumference data among women with pregnancy outcome data
Comparison with external comparator (Pfizer Study C4951006)	Live births who are SGA based on weight among women with pregnancy outcome data	Live births among women with pregnancy outcome data
Postnatal growth deficiency		
Primary analysis between internal cohorts (at 2, 4, 6, and 12 months)	Singleton infants without MCMs who were not born preterm or SGA with postnatal growth deficiency based on weight/length/head circumference among infants with weight/length/head circumference data at the time point	Singleton infants without MCMs who were not born preterm or SGA with weight/length/head circumference data at the time point
Infant developmental delay	-	
Primary analysis between internal cohorts (at 2, 4, 6, and 12 months)	Infants without MCMs who were not born preterm with developmental delay in a particular category among infants with developmental milestone data for the category at the time point	Infants without MCMs who were not born preterm with developmental milestone data for the category at the time point

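### Size at birth is compared between cohorts only as SGA yes/no; a supportive birth-weight z-score comparison on data already collected would detect small growth shifts much better

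*Protocol*

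**What the plan says.** Section 7.2 reports that high oral doses in animals "resulted in adverse effects on development in rats (decreased fetal body weight and increased incidence of fetal variations"). It adds that these exposures were over 200 times the human therapeutic exposure and were toxic to the mothers.

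At pregnancy outcome the registry collects gestational age and "Fetal/infant characteristics, including sex, birth weight, length, head circumference" (section 9.4.1.2). Section 9.3.4.8 defines SGA as birth weight below the 10th percentile for sex and gestational age. It fixes the reference: "For the determination of SGA, the registry will utilize the sex-specific international growth reference standards from the" INTERGROWTH-21st consortium, for births from 24 weeks 0 days to 42 weeks 6 days.

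The comparison methods in section 9.7.3.1 are written for binary outcomes:
- Unadjusted: "Exact methods will be used to calculate crude (unadjusted) relative risks for binary outcomes", with SGA on the list.
- Adjusted: "For each binary outcome, a weighted generalized linear model using a binomial family and a log (relative risk) link will be employed" to estimate a relative risk.

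The Table 4 numerator for the internal SGA comparison is "Singleton live births without MCMs who are SGA based on weight/length/head circumference among women with pregnancy outcome data". For measured values, section 9.7 says: "For each continuous variable, the number of observations, median, mean, standard deviation, minimum, and maximum will be reported". That is a summary by cohort, not a comparison.

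**The concern.** An exposure that slows fetal growth would be expected to move the whole birth-weight distribution, not only the part near the 10th percentile. Cutting a standardised weight at one point discards most of the information about such a shift. The plan already needs each infant's position on a sex- and gestational-age-specific standard to decide SGA status, and then uses only which side of the cut the infant falls on.

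No other planned outcome fills the gap. Postnatal growth deficiency is also a 10th-percentile cut, and section 9.7.3.3 removes infants born preterm or SGA from its denominator. At stake is how a null SGA relative risk would be read: next to a stated power above 99%, it could be taken as excluding growth effects that the analysis has little chance of seeing.

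**Working it through.** **Inputs from the protocol.** "The full study will aim to prospectively enroll a minimum of 390 women with migraine who were exposed to rimegepant", with the same number unexposed (section 9.5.2). Evaluable: 390 × 0.9 × 0.9 = 315.9, stated as 316 per cohort. SGA reference rate 10%, two-sided alpha 0.05, normal approximation, 2.5-fold rise (Table 3).

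**Assumptions not in the protocol.** Normal z-scores with SD 1, a uniform downward shift s, and no variance inflation from weighting.

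**Formulas.**
- Power for two proportions: Φ{[|p1 − p0|√n − 1.96√(2p̄(1 − p̄))] / √(p0(1 − p0) + p1(1 − p1))}, where p̄ is the mean of p0 and p1.
- SGA rate after a shift: p1 = Φ(−1.2816 + s).
- Power for the mean z-score: Φ(s√(n/2) − 1.96).

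**Reproducing the plan.**
- MCM, 3% vs 7.5%, n = 390: 80.6% (stated 80.6%).
- MCM, 3% vs 8.1%, n = 316: 80.1% (stated 80%).
- SGA, 10% vs 25%, n = 390: 99.99% (stated above 99%).

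**What a 2.5-fold rise means.** Φ⁻¹(0.25) − Φ⁻¹(0.10) = −0.6745 + 1.2816 = 0.607 SD.

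**Worked case, s = 0.20, n = 316.** p1 = Φ(−1.0816) = 0.1397, a relative risk of 1.40.
- SGA: [0.0397 × 17.776 − 1.96 × 0.4593] / 0.4585 ≈ −0.42, power 34%.
- Mean z-score: 0.20 × 12.570 − 1.96 = 0.554, power 71%.

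**All shifts at 316 per cohort.**

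| Shift (SD) | SGA rate | RR | Power, SGA | Power, mean z |
|---|---|---|---|---|
| 0.20 | 14.0% | 1.40 | 34% | 71% |
| 0.25 | 15.1% | 1.51 | 49% | 88% |
| 0.30 | 16.3% | 1.63 | 65% | 96.5% |
| 0.40 | 18.9% | 1.89 | 89% | >99% |
| 0.50 | 21.7% | 2.17 | 98% | >99% |

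The shift detectable with 80% power is 0.35 SD through SGA (RR 1.77). Through the mean it is (1.96 + 0.842) × √(2/316) = 0.22 SD.

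**Sensitivity.**
- At all 390 per cohort: 40% vs 80% at 0.20 SD and 58% vs 94% at 0.25 SD.
- At an assumed 290, since the SGA analysis is limited to singletons without MCMs: 31% vs 67% and 46% vs 85%.
- At 316 with an assumed comparator SGA rate of 5% to 7%: SGA power is 24% to 29% at 0.20 SD, 36% to 42% at 0.25 SD and 49% to 57% at 0.30 SD.

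**The case against.** The strongest objection is that this is material for the statistical analysis plan. Section 9.7 defers detailed methodology there and lets it modify the protocol's plans, and nothing forbids a supportive continuous analysis. That is fair as far as it goes: no figure is wrong and nothing is contradicted. But the choice of scale is not left open. The outcome list, the methods in section 9.7.3.1 and Table 4 all fix size at birth as a binary comparison.

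Several other points stand and limit the finding:
- **Gestational age.** SGA already accounts for it, and preterm birth is compared separately, so no planned comparison confuses early birth with slow growth.
- **External comparison.** The companion retrospective study supplies SGA rates, which is a reason to keep SGA.
- **Intervals.** Relative risks are reported with 95% confidence intervals, so an imprecise null would show its width to a careful reader.
- **Sizing.** The study is sized on MCM, and secondary p-values are declared nominal.

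A reader might infer that any moderate growth effect would probably be missed. The figures do not support that: on the base assumptions SGA has 65% power at 0.30 SD and 98% at 0.50 SD. A reader might also infer that birth weight will be shown only as an unstandardised mean. Section 9.7 gives a general rule for continuous variables, which includes the median and SD, and does not say how birth weight will be displayed.

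**Conclusion.** The point holds as an inexpensive improvement. At the protocol's own evaluable number, a shift of 0.20 to 0.25 SD would be missed at least about half the time through SGA alone (power 34% to 49%). A mean z-score comparison in the same infants has 71% to 88% power. Above about 0.30 SD the case weakens, because SGA by then detects the shift more often than not.

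The figures rest on the assumptions stated above. Weighting would lower the power of both analyses. The 0.25 SD result depends on the number evaluable: with all 390 per cohort, SGA power there is 58%. A comparator SGA rate below 10% would strengthen the case. The protocol does not say what size of shift matters clinically.

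The rat finding should not be read as evidence of human harm, given the exposure margin and the maternal toxicity. It is a reason to analyse birth weight efficiently. The Table 3 entry for SGA is correct for the effect it names.

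**What to change.** Keep SGA as the secondary outcome. In section 9.7.3.1 and Table 4, add one supportive internal-cohort analysis of the INTERGROWTH-21st birth-weight z-score, specific to sex and gestational age. Use the same singleton live births and the same stabilised inverse-probability weights, and report the weighted mean difference with a robust 95% confidence interval. Label it supportive, and state how births outside the gestational range of the standard are handled.

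While editing, reconcile section 9.3.4.8, which defines SGA by birth weight alone, with the Table 4 row, which also refers to length and head circumference.

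The cost is a few lines of text and one weighted linear model. No new data, participants or visits are needed. The downside is one more nominal secondary p-value.
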